- Presence of one or more of the following physiological states: systolic BP <90 mmHg, or MAP <65 mmHg, or increasing need for vasopressor drug infusion or pulse pressure variation >12 % or stroke volume variation >12%, or Cardiac index <2.2 L/min/m² or heart rate >100 or urinary output <20 ml/hr or either rising lactate levels or lactate levels >2 mmol/L or capillary refill time >3 seconds or central venous pressure <8 mmHg.

Exclusion criteria

- Confirmed or suspected pregnancy
- Patients with traumatic brain injury
- Active bleeding
- Haemoglobin level <70 g/L

• People who refuse blood products SWIPE Protocol UK V2.2, dated 18th May 2016 EudraCT No: 2016-001940, UK Protocol ID: R04336 • Patients in whom death is considered imminent (within 24 hours)

Sample size estimate

Given that in the first 48 hours the 5% albumin administered in the SAFE study [14] was a total of 1785ml (SD of 1865), we will aim to detect a decrease in fluid given to 1300ml (SD of 1368: proportionately the same as that seen in SAFE for a mean inout of 1785ml). This decrease of around 500ml in fluid input is considered of potential clinical value. To have a 90% power of detecting such a difference at an alpha level of 0.05, 195 patients will need to be randomised to each group. We have rounded this number up to 200 in each group to account for possible data loss.

Randomisation procedure

- Computer generated sets of random allocations will be produced by the Research Co-ordinator in advance of the study.
- Randomization will be by means of sealed envelopes with permuted blocks of variable size.
- Each envelope will contain a study arm allocation as well as a copy of a simplified version of the study protocol.
- Every patient who participates in any study related procedure will be assigned a unique patient number.

Intervention description

Patients will be randomised one of two arms:

• The treatment arm will receive an intravenous infusion of 20% albumin (Alburex

20®, CSL Behring, Marburg, Germany) every time the treating clinician decides SWIPE Protocol UK V2.2, dated 18th May 2016 EudraCT No: 2016-001940, UK Protocol ID: R04336 that a fluid bolus needs to be given during the first 48 hours in ICU. The treating clinician determines the volume and infusion rate of each fluid bolus.

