- Reason for admission to intensive care (post-operative complication, sepsis, medical emergency, post-operative management, other) and urgency (planned, unplanned, emergency). If surgical, date and type of operation.
- Weight and height on admission, to be used for calculation of body surface area.

Clinical Data

- Haemodynamic data: HR, ABP, CVP will be measured hourly during the study period.
- Blood gas results: PaO₂, lactate concentration, pH/H+ concentration, bicarbonate concentration, sodium concentration, chloride concentration, creatinine concentration, haemoglobin concentration and base deficit/excess will be measured hourly during the study period.
- Fluid balance Resuscitation fluids. Each fluid bolus will be recorded (type of resuscitation fluid, volume, infusion speed).

• Fluid balance – for each day or part there of. SWIPE Protocol UK V2.2, dated 18th May 2016 EudraCT No: 2016-001940, UK Protocol ID: R04336

- Baseline serum creatinine and urea pre-admission to ICU if available. Defined as
 a serum creatinine and urea taken in the six months pre-admission to hospital for
 this ICU event.
- Serum creatinine on admission, as indicated above, and as indicated clinically.
- Serum albumin on admission and as indicated clinically.
- Doses of furosemide administered (or rate of furosemide infusion).
- Doses of vasopressors and inotropes administered (or infusion rates).
- All other biochemical and haematological indices recorded as clinically indicated during the patient admission.

Outcome Data

- Primary efficacy outcome
 - Amount of resuscitation fluid (mL) administered over the first 48 hours in ICU.
- Secondary efficacy outcomes
 - The cumulative fluid balance after 48 hours in ICU.
 - The amount of vasoactive medication given over the first 4 hours after a fluid bolus and over the first 48 hours in ICU.
 - The total amount of fluids given over the first 4 hours after a fluid bolus,
 daily and over the first 48 hours in ICU.
 - The relative change in haemodynamic variables and blood gas results over the first 4 hours after a fluid bolus.
 - The relative change between baseline and peak creatinine in the first 48

hours after randomization.

- Patient-centred efficacy outcomes
 - Need for RRT
 - Renal status at 90 days
 - Hours on mechanical ventilation
 - ICU discharge status (alive or dead)
 - ICU length of stay
 - Hospital discharge status (alive or dead)

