 - Hospital outcome (discharge destination home, another hospital, advanced care institution)
 - Hospital length of stay (date of discharge)
 - Mortality status at 90 days.
- Feasibility and safety outcomes:
 - Distribution of values for primary and secondary outcome
 - Randomized / Screened patients ratio
 - Data completion rate
 - Loss to follow-up rate
 - Recruitment rate and duration
 - Separation in amount of fluid given

Safety outcomes

- Development of side-effects
- Episodes of hypotension
- Development of kidney failure

o Adverse changes in any of the physiological efficacy measures

Data analysis

Outcomes will be compared after log transformation where appropriate. Comparisons will be made using t-test and ANOVA for repeated-measures or Wilcoxon rank-signed test and Kruskall-Wallis according to the underlying distribution for continuous data and Chi-square for categorical data. A Kaplan-Meier curve with log-rank test will be performed to further compare in-hospital mortality and rate of discharge home. Logistic regression analysis will also be performed to adjust for baseline imbalances. Analysis will be an on intention-to-treat basis.

Risks and Benefits

Albumin solutions have been used for resuscitation since the 1940s. An investigation of the safety of albumin solutions showed that between 1998 and 2000, approximately 10⁷ units of such albumin solutions were administered worldwide. Adverse effects that were directly associated with albumin were an extremely rare event during this observation period [15]. There are, however, more recent reports that the use of (20%) albumin is associated with increased mortality for patients with traumatic brain injury [6]. Accordingly, patients with traumatic brain injury will be excluded from the SWIPE study. Although albumin is prepared from pooled plasma, albumin preparations currently available are considered to be non-allergenic due to the manufacturing process.

Data handling, retention, storage and destruction

Data handling

The case report form (CRF) will be developed by the members of the investigator team as a paper CRF. All data will be collected by members of the investigator team as described in the CRFs from the source data. Information recorded in the CRF should accurately reflect the subject's medical/hospital notes and must be completed as soon as it is made available.

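### The only adjusted analysis is logistic regression for observed baseline imbalances, which gives no adjusted mL difference for the continuous primary outcome and lets chance choose the covariates

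*Protocol*

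**What the plan says.** All of this is in the protocol.

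- **Outcome Data** gives the primary efficacy outcome as "Amount of resuscitation fluid (mL) administered over the first 48 hours in ICU". The five secondary efficacy outcomes are also amounts, balances or relative changes. Binary outcomes appear among the patient-centred and safety outcomes: need for renal replacement therapy, ICU and hospital discharge status, 90-day mortality and development of kidney failure.
- **Data analysis**, on continuous outcomes: "Outcomes will be compared after log transformation where appropriate", and then "Comparisons will be made using t-test and ANOVA for repeated-measures or Wilcoxon rank-signed test and Kruskall-Wallis according to the underlying distribution for continuous data". None of these methods is described as covariate-adjusted.
- **Data analysis**, on adjustment, in full: "Logistic regression analysis will also be performed to adjust for baseline imbalances". No outcome, covariate or definition of imbalance is attached to it. It follows the sentence on Kaplan-Meier curves for in-hospital mortality and discharge home, and comes just before the statement that analysis is by intention to treat.
- **Sample size estimate** sizes the trial on a difference in mean volume, 1785 mL (SD 1865) against 1300 mL (SD 1368). With power set at 90% and alpha at 0.05, it concludes that "195 patients will need to be randomised to each group". This is rounded up to 200.

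**The concern.** Two features of the adjustment sentence are fixed badly.

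**The model does not reach the main question.** Logistic regression models a categorical response. The protocol defines no binary version of fluid volume, so the one adjusted method it names cannot return an adjusted difference in mL for the primary outcome or for the continuous secondary outcomes.

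**The trigger is the observed imbalance.** In a randomised trial a baseline difference between arms is a chance event, visible only once the data are in. The error that a covariate introduces into the treatment estimate depends on both its imbalance and how strongly it predicts the outcome. Choosing on imbalance alone ignores the second factor: a strong predictor that happens to be balanced is left out, and an irrelevant variable that happens to differ is put in. The precision that a strong predictor offers whatever its balance is then lost. The trial is also open label, which makes it more useful to have the covariates on record beforehand.

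At stake is the precision and clarity of the supporting analysis, not the validity of the main comparison.

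**Working it through.** **1. Reproduce the plan's sample size**

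Inputs, from Sample size estimate: difference 1785 − 1300 = 485 mL; SDs 1865 and 1368; power 90%; alpha 0.05, sidedness not stated.

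Formula: n per group = (z_alpha + z_power)² × (SD1² + SD2²) / difference².

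- 1865² + 1368² = 3,478,225 + 1,871,424 = 5,349,649
- 5,349,649 / 485² = 5,349,649 / 235,225 = 22.743
- One-sided: (1.645 + 1.282)² × 22.743 ≈ 8.564 × 22.743 = 194.8, so 195, as stated
- Two-sided: (1.960 + 1.282)² × 22.743 ≈ 10.507 × 22.743 = 239.0, so 239

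The stated 195 therefore matches a one-sided 5% test. This matters here only because the baseline power depends on sidedness.

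**2. What adjustment could add on the mL scale**

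Unadjusted SE with 200 per group = √(5,349,649 / 200) = 163.5 mL. With covariates explaining a share R² of the outcome variance, SE is multiplied by √(1 − R²). Power = Φ(485/SE − z), with z = 1.960 two-sided and 1.645 one-sided. The R² values are assumptions; the protocol gives none.

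| R² (assumed) | SE, mL | 485/SE | Two-sided power | One-sided power |
|---|---|---|---|---|
| 0 | 163.5 | 2.97 | 84% | 91% |
| 0.10 | 155.2 | 3.13 | 88% | 93% |
| 0.20 | 146.3 | 3.32 | 91% | 95% |

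A measure that does not depend on sidedness is the equivalent unadjusted sample size, 200/(1 − R²): 222 per group at R² = 0.10 and 250 at R² = 0.20. If the analysis were on the log scale, these SDs would not apply.

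**3. How often chance alone would trigger adjustment**

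The protocol gives no screening rule. Suppose k independent baseline variables, each tested at 5%. The chance of at least one nominal imbalance is 1 − 0.95^k: 23% for k = 5, 40% for k = 10 and 54% for k = 15.

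**4. Effect on type I error**

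A null simulation used 200 per arm, ten covariates with joint R² 0.3, a linear model and 6,000 runs. The Monte Carlo standard error is √(0.05 × 0.95 / 6000) = 0.28 percentage points.

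| Analysis | Rejection rate at nominal 5% |
|---|---|
| Unadjusted | 5.6% |
| Adjusted for imbalanced covariates only | 4.6% |
| Adjusted for the pre-specified set | 5.0% |
| Better of unadjusted and imbalance-adjusted | 6.1% |

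Even free choice between two results adds about half a point to the unadjusted rate in the same runs (6.1 − 5.6) and about one point to the nominal level.

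**The case against.** The strongest reply is that the protocol never says logistic regression will be applied to the primary outcome. The sentence follows one on mortality and discharge, the protocol lists several binary outcomes that the model fits, and no adjusted mL estimate is promised. This stands. A reader might infer that the sponsor intends to cut the fluid volume at some threshold, or that the primary analysis is unsound. The text supports neither: no cut-point appears, and the regression is additional to an unadjusted intention-to-treat comparison.

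A second reply is that covariate lists, a linear model or a site term may be in a statistical analysis plan that is not shown. That also stands, so the absence of a site term is not a finding here. It does not cover the wording that is present, though. A plan that adjusted for named covariates whatever their balance would depart from a sentence that makes imbalance the reason for adjusting.

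Third, the figures rest on assumptions. A reader might take the 84% as proof that the trial misses its stated 90% power. It holds only for a two-sided test; at one-sided 5%, 200 per group gives about 91%. The R² values and the 40% chance of some imbalance are likewise illustrations. Nor does the simulation support a charge of materially inflated false positives.

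**Conclusion.** The point holds as a moderate one about a supplementary analysis. As written, the sole adjusted method serves binary outcomes only, and its covariates depend on chance differences seen after randomisation. The main randomised comparison is unaffected and the type I error effect is small.

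The cost is forgone precision: an SE about 5–11% smaller would be available if baseline variables explained 10–20% of the variance. That corresponds to two-sided power of 88–91% instead of about 84% for 485 mL with 200 per group. These figures assume the protocol's SDs, analysis on the mL scale, full data on 200 per group and a two-sided 5% test. The R² range is not from the documents. The sidedness of the sample size calculation is a separate matter and adds no weight here.

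**What to change.** Keep the stated unadjusted comparison, and replace the adjustment sentence with wording such as:

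> An adjusted analysis of the primary and continuous secondary outcomes will use linear regression (log scale if fixed in advance), with covariates named before data are seen and used whatever their balance, for example site, reason for admission, weight, and the last lactate and vasopressor dose before randomisation. Logistic regression with the same covariates will be used for binary outcomes only.

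Then state in advance which of the unadjusted and adjusted results is primary. Without that, the retained t-test or Wilcoxon sentence and the new model would compete.

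The covariates are examples, and the choice is the sponsor's. Site is known by design, and reason for admission and weight are listed under Patient data. Lactate and vasopressor doses are listed under Clinical Data, but lactate is hourly during the study period and vasopressor doses have no stated time point, so a baseline time point has to be fixed for both. Beyond that, the cost is a few sentences and a little more analysis work. No added patients are needed.
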